error of 0.05, the critical value for the interim analysis will be 0.0054 and the final critical value will be 0.0492. With a sample size of 900 per group and  $\alpha=0.0492$ , the power to detect a 32% reduction in COVID-19 disease rate (10% vs 6.8%) between the placebo group and each HCQ treated group would be 87%. Power calculations are also given for placebo rates of 8% and 15% with a 32% reduction in COVID-19 disease rates for the HCQ treated groups. Assuming 5-10% of patients will have SARS-CoVID-2 viremia positive at the baseline, we need 1000 per group with a total of 3000 patients to complete the trial.

Power calculations using simulations for Dunnett’s step up method

Assuming 900 per group and  $\alpha=0.0492$

COVID-19 disease rate in placebo	COVID-19 disease rate in treatment	Power
8%	5.4%	80%
10%	6.8%	87%
15%	10%	98%

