6.3.4.4 Secondary Aims, Hypotheses and Analyses

S1: To compare the rates of SARS-CoV 2 infection status between the randomized treatment arms and the control arms to determine the effect of HCQ dose in the prevention of COVID-19 viremia and disease.

Secondary Hypothesis (S1): There is a hydroxychloroquine dose effect on acquisition of SARS-CoV 2 infection status, compared to placebo.

The endpoint will be SARS-CoV 2 infection status, defined as 1) no SARS-CoV 2 test positive during study follow up; 2) SARS-CoV 2 test positive (i.e., at least one positive RT PCR, or both IgM and IgG positive serology) without clinical symptoms (“asymptomatic SARS-CoV 2 test positive”) 3) SARS-CoV 2 test positive with clinical symptoms (“symptomatic SARS-CoV 2 test positive”).

The analysis will be conducted using FAS. Ordinal logistic regression will be used and analysis will start testing the overall daily and weekly dose effect, followed by pairwise/subgroup comparisons if an overall dose effect is detected at 0.05 level.

S2: To compare the rates of SARS-CoV 2 infection status in the non-randomized comparator arm to the randomized groups to assess the impact of chronic weight-based dosing of HCQ for COVID-19 prevention.

Secondary Hypothesis (S2): There is weekly /daily HCQ dose effect on acquisition of SARS-CoV 2 infection, compared to patients who were already on HCQ.

The endpoint will be the same as described for S1. The analysis will include all randomized *in FAS and non-randomized study participants with at least one post-baseline follow-up.*

We will first test for treatment selection bias using the data collected at the baseline. Inverse probability treatment weighting (IPTW)/propensity score, or matched sub-cohort will be considered to adjust for imbalanced participant characteristics. A similar analysis to that of S1 will be used for testing hypothesis S2.

S3: To compare the rate of SARS-CoV 2 infections as measured by serum IgM/IgG in participants receiving HCQ versus placebo.

Secondary Hypothesis (S3): There is weekly /daily dose effect on status of SARS-CoV 2 infection as measured by serum IgM/IgG, compared to placebo.

The endpoint will be serum IgG/IgM status at each participant’s study conclusion, classified as:

1. Negative (consistently negative for both serologies)
2. Indeterminate (IgM positive, with IgG consistently negative)
3. Positive (IgM and IgG positive, or IgG positive)

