6.4 Sample size/power calculation

Power Calculation for original Primary Aim: (based on original Study Protocol, dated 04/06/2020)

To determine if the use of hydroxychloroquine as preventive therapy decreases the rate of acquisition of SARS-CoV 2 infections in Study Participants as compared to placebo.

The sample size and power calculation for the original aim are based on a SARS-CoV 2 infection rate of 10% in the placebo-treated group, and an average of 6.8% in the randomized weekly- and daily- HCQ groups, with a relative reduction of 32%. Based on an alpha=0.05 two-sided test, with 900 subjects per group that are COVID negative at the baseline, and one interim analysis when 50% of participants (450 per group) have completed the study and primary

endpoint data assessment, we will have more than 80% power (82% to be exact using nQuery) to detect a significant HCQ effect if the observed test statistic is ± 2.9626 or $p\text{-value} < 0.003$ in the interim analysis, or ± 1.9685 or $p\text{-value} < 0.0497$ in the final analysis, using an O'Brien-Fleming alpha spending method to ensure an overall type 1 error of 0.05 and assuming that overall COVID positive rate in the weekly- and daily- dose HCQ groups is 6.8% with $n=1800$ in the HCQ treated group and 900 in the placebo treated group. A reduction of 36% can be detected between either one of the HCQ treatment groups and placebo, using the same assumptions. Assuming 5-10% of patients will have SARS-CoV 2 positive at the baseline, we need 1000 per group, with a total of 3000 participants to complete the trial.

Power Calculation for revised Primary Aim: (based on revised Study Protocol dated 04/16/2020 or after)

To determine if the use of hydroxychloroquine as preventive therapy decreases the rate of acquisition of SARS-CoV 2 infections with clinical COVID-19 disease in Study Participants for each randomized treatment arm as compared to placebo.

The revised sample size and power calculation are based on a 10% rate of clinical COVID-19 disease (with laboratory confirmation) in the placebo-treated group, and an average 6.8% rate in the two randomized HCQ-treated groups (weekly and daily dosing groups), with a relative reduction of 32%. We propose two looks; one look (interim analysis) when 50% of the participants have completed the study and primary endpoint assessment (for P1), and a final look when 100% of participants have completed the study.

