Based on an $\alpha=0.05$ two-sided test, chi-square test/logistic regression with odds ratio estimates, and Haybittle-Peto alpha spending method to ensure an overall type I error, the critical value for the interim analysis will be 0.001 and the critical value for the final analysis will be 0.05. For data illustration, we have also included an O'Brien-Fleming spending function approach for controlling type I error with a critical value of 0.0054 for the interim analysis and 0.0492 for the final analysis.

Power calculations are based on $n=900$ or 935 participants per study arm, using a simulation approach ($n=10,000$ simulations) in three correction methods: #1 comparing the weekly and daily HCQ dose arms to the placebo group separately using the Dunnett's step-up approach; #2 comparing the weekly and daily HCQ dose arms to placebo separately using a conservative Bonferroni approach with critical value of 0.025 for each test at the final look; #3 comparing the combined weekly and daily HCQ dose arms to the placebo using a single test.

With Haybittle-Peto boundary and $\alpha=0.05$ at the final look, the Dunnett's step-up correction uses a closed gatekeeping strategy for testing the daily dose arm vs placebo and the weekly dose arm vs placebo separately: the largest p value tested first will be at 0.05; if that fails, the second test will be at p value 0.026, delivered from the last row of Table 2 of Dunnett and Tamhane (1992), and validated based on simulation using R *DunnettTests* package. Likewise, at the interim look, the largest p value tested first will be at 0.001; if that fails, the second test will be at 0.0005.

Table 1. Power for different scenarios using varying methods. Sample size was determined using the Dunnett's Step up method with the Haybittle-Peto boundary.

Haybittle-Peto approach	$p_0=0.1, p_1=0.073, p_2=0.063$		$p_0=0.1, p_1=p_2=0.068$	
Method	n=900	n=935	n=900	n=935
#1 Dunnett's Step up	0.800	0.811	0.770	0.800
#2 Bonferroni	0.784	0.800	0.745	0.760
#3 Daily+weekly arms vs placebo	0.812	0.83	0.819	0.835

p_0 is the rate for the placebo treated group and p_1 and p_2 are the rates for the two treated groups.

O'Brien-Fleming approach	$p_0=0.1, p_1=0.073, p_2=0.063$		$p_0=0.1, p_1=p_2=0.068$		
Method	n=910	n=935	n=900	n=935	n=970
#1 Dunnett's Step up	0.8	0.814	0.76	0.776	0.801
#2 Bonferroni	0.787	0.8	0.741	0.761	0.784
#3 Daily+weekly arms vs placebo	0.815	0.83	0.815	0.83	0.846

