p_0 is the rate for the placebo treated group and p_1 and p_2 are the rates for the two treated groups.

For the primary Aim / hypothesis, we will use Dunnett's Step up approach to test each dose effect vs. placebo, and a sample size of 935 per arm will insure at least 80% power. The power will be higher for some of the secondary Aims (S1-S4 if use the compressed binary endpoint of infection presence or absence), since a single test will be used to study overall dose effect first, followed by subgroup analysis (Correction Method #3)

Assuming 5-10% of patients will be excluded from FAS, we need 1000 subjects per group, with a total of 3000 participants to complete the trial. The power and sample size calculation remained unchanged.

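### The SAP's 80% power rests on an unsupported 10% placebo rate carried over from a broader endpoint, and the Protocol's power table overstates power for the planned two-sided test

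*SAP*

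**What the plan says.** SAP 6.4 gives two power calculations. The one for the original aim is "based on a SARS-CoV 2 infection rate of 10% in the placebo-treated group", with an average of 6.8% on hydroxychloroquine. The one for the revised aim reads: "The revised sample size and power calculation are based on a 10% rate of clinical COVID-19 disease (with laboratory confirmation) in the placebo-treated group", again with an average of 6.8% in the treated arms. The section closes by saying that the calculation did not change.

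The revised calculation uses a "two-sided test, chi-square test/logistic regression with odds ratio estimates", Dunnett's step-up rule for the two doses and a Haybittle-Peto interim look. Table 1 varies the treated-arm rates, the sample size, the boundary and the correction method. The placebo rate is 0.10 in every column. The SAP concludes that "a sample size of 935 per arm will insure at least 80% power", and then: "Assuming 5-10% of patients will be excluded from FAS, we need 1000 subjects per group".

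Protocol 8.3 uses 900 per arm, the step-up rule and O'Brien-Fleming critical values of 0.0054 and 0.0492. It says power for 10% versus 6.8% "between the placebo group and each HCQ treated group would be 87"%. It adds: "Power calculations are also given for placebo rates of 8% and 15% with a 32% reduction". The three tabulated powers are 80% (8% vs 5.4%), 87% (10% vs 6.8%) and 98% (15% vs 10%). The Protocol does not say whether the test is one- or two-sided.

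**The concern.** The revised endpoint is narrower than the original one. Secondary analysis S1 in SAP 6.3.4.4 has a separate category for participants with "at least one positive RT PCR, or both IgM and IgG positive serology) without clinical symptoms"; they count as infected but not as primary events. Unless every infection is symptomatic, the placebo rate for the revised endpoint is below the infection rate. Keeping 10% may be reasonable, but the SAP gives no reason for it.

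Power here is driven mainly by the number of placebo events: about 94, 75 and 47 expected among 935 participants at 10%, 8% and 5%. A reader who wants to know what happens below 10% finds nothing in the SAP. The one table that addresses it, in Protocol 8.3, conflicts with the SAP at the point where the two can be compared. The risk is that a null result is read against a power figure that the planned test does not have.

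**Working it through.** **Inputs.** Rates, sample sizes and critical values come from SAP 6.3.4.3, 6.4 and 6.7 and from Protocol 8.3. Placebo rates other than 10% are an assumed range.

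**Rule simulated.** For each dose against the shared placebo arm, z = (p̂0 − p̂1) / √(2p̄(1 − p̄)/n), with a two-sided p-value. Interim at n/2: success if the larger p < 0.001, otherwise if the smaller p < 0.0005. Final: success if the larger p < 0.05, otherwise if the smaller p < 0.0262. Power is the share of simulated trials with at least one dose declared effective. There were 300,000 runs per case, and 1,000,000 for the equal-effects step-up cells of Table 1.

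**Hand check of one comparison** (10% vs 6.8%, n = 935, two-sided 0.05, no interim). p̄ = 0.084. Null SE = √(2 × 0.084 × 0.916/935) = 0.01283. Alternative SE = √((0.1 × 0.9 + 0.068 × 0.932)/935) = 0.01281. Power = Φ((0.032 − 1.96 × 0.01283)/0.01281) = Φ(0.535) = 0.70. The figures below are higher because either dose may succeed.

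**Step 1: reproduce SAP Table 1 (placebo 10%).**

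| Method | Treated rates | n | SAP | Recomputed |
|---|---|---|---|---|
| Step-up, Haybittle-Peto | 7.3% / 6.3% | 900 | 0.800 | 0.800 |
| same | 7.3% / 6.3% | 935 | 0.811 | 0.815 |
| same | 6.8% / 6.8% | 900 | 0.770 | 0.763 |
| same | 6.8% / 6.8% | 935 | 0.800 | 0.781 |
| Bonferroni, Haybittle-Peto | 6.8% / 6.8% | 900 | 0.745 | 0.747 |
| same | 6.8% / 6.8% | 935 | 0.760 | 0.761 |
| Step-up, O'Brien-Fleming | 6.8% / 6.8% | 900 | 0.76 | 0.765 |
| same | 6.8% / 6.8% | 935 | 0.776 | 0.779 |
| same | 6.8% / 6.8% | 970 | 0.801 | 0.795 |

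The model is the SAP's own. Only the 0.800 cell is off by more than one point. With the SAP's 10,000 runs the simulation error is √(0.8 × 0.2/10,000) = 0.004, so the 0.019 gap is nearly five standard errors. With equal effects under Haybittle-Peto, 970 per arm gives 0.796 and about 985 gives 0.800.

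**Step 2: vary the placebo rate (SAP rule, Haybittle-Peto).**

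| Placebo rate | Equal 32% reduction, n = 935 (n = 900) | Reductions of 27% / 37%, n = 935 (n = 900) |
|---|---|---|
| 15% | 0.930 (0.921) | 0.950 (0.943) |
| 10% | 0.781 (0.763) | 0.815 (0.800) |
| 8% | 0.676 (0.660) | 0.713 (0.695) |
| 5% | 0.469 (0.454) | 0.497 (0.482) |

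The 27% / 37% column scales the SAP's 7.3% / 6.3% scenario. The n = 900 figures are what 1,000 per arm leaves at the SAP's upper exclusion rate: 1,000 × 0.90 = 900.

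**Step 3: the Protocol table** (n = 900; 0.0054 and 0.0492; second-step values of 0.0027 and 0.0258 assumed, since the Protocol gives none).

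| Rates | Protocol | Two-sided | One-sided | Stated minus two-sided |
|---|---|---|---|---|
| 8% vs 5.4% | 80% | 0.675 | 0.781 | 12.5 points |
| 10% vs 6.8% | 87% | 0.766 | 0.852 | 10.4 points |
| 15% vs 10% | 98% | 0.941 | 0.971 | 3.9 points |

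The middle row needs no simulation. SAP Table 1 gives 0.76 for the same rates, sample size, method and critical values.

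**Step 4: what 10% requires.** Protocol section 1 puts infection among healthcare workers at up to 10–30%. A 10% symptomatic rate then needs 10/30 = 33% of infections symptomatic at the top of that range, 10/20 = 50% at 20%, and 10/10 = 100% at the bottom. The same section says up to 85% may be asymptomatic or minimally symptomatic. That figure does not yield a rate, because some minimally symptomatic cases could meet the SAP's definition.

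**The case against.** - **The 10% is openly a premise, and nothing shows it is too high.** The SAP names the revised endpoint when it states the rate, and every Table 1 column is headed with it. The symptom threshold in SAP 6.3.1 is low (fever, or two or more new non-fever symptoms), and every test-positive participant is followed for at least 30 days for symptoms. Both raise the symptomatic share. This stands: the 10% is unsupported, not disproved, and the 8% and 5% rows are assumptions.
- **A wrong placebo rate was foreseen.** Protocol 4 and 8.3 and SAP 6.1, 6.4.1 and 7 allow reassessment at the interim look. This mitigates the problem only in part, because no threshold, rule or maximum sample size is given.
- **The Protocol appears to be the older text, and the SAP already carries the lower figure.** That may explain the conflict. It does not correct the Protocol table, which remains the only one showing other placebo rates.
- **One-sidedness is inferred.** True, and the one-sided figures miss the stated ones by 1 to 2 points. The conclusion does not need that inference: the table disagrees with the two-sided test and with the SAP, whatever its origin.
- **A two-point gap in one cell is small, and 80% holds in the SAP's other scenario.** Both are right: 7.3% / 6.3% gives 0.815 at 935. But the SAP's sentence is unconditional, and its own O'Brien-Fleming table, shown for illustration, has 0.776 at 935 with equal effects.
- **A null result is read from the estimate and its interval, and the fix changes no test or patient.** Fair, and it limits the weight of the point. The power statements are still wrong as written.

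**Conclusion.** The concern holds, with high confidence, as something that should be fixed.

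- The 10% versus 6.8% assumption was carried from any infection to a subset of it, without a stated basis.
- The claim of at least 80% power at 935 per arm holds at placebo rates of about 10% and above. At exactly 10% with equal effects it is about 0.78. Below 10% it fails: 0.68 to 0.71 at 8% and 0.47 to 0.50 at 5% across the SAP's two effect patterns.
- The Protocol 8.3 table overstates two-sided power by about 4 to 13 points.

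These figures assume the SAP's step-up rule with one look at half the participants, power defined as at least one dose significant, relative reductions held constant as the placebo rate changes, and, for the Protocol table, the second-step values given above. Whether the true symptomatic rate is below 10% cannot be settled from the documents.

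**What to change.** 1. In SAP 6.4, give the basis for 10% on the symptomatic, laboratory-confirmed endpoint, or label it an assumption.
2. Make the 935-per-arm sentence conditional, for example: *If the placebo rate of clinical COVID-19 with laboratory confirmation is 10% (assumed), 935 per arm gives about [value from the rerun] power for at least one dose; power at other assumed placebo rates is shown in Table 1.*
3. Rerun the SAP's simulation over a range of placebo rates for both existing effect scenarios, add the rows to Table 1, and recheck the 0.800 cell. Values to check against, for a 32% reduction in both arms at 935: about 78%, 68% and 47% at 10%, 8% and 5%.
4. Replace the Protocol 8.3 table and its 87% statement with figures from the same two-sided rule, boundary and sample size as the SAP.

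The cost is one simulation rerun, one extended table, one replaced table with its accompanying power statement, and one reworded sentence. Stated power becomes less favourable: about 78% instead of 80% in the SAP's equal-effects case. At 900 per arm with the Protocol's own boundary, the 80% and 87% entries would fall to about 67.5% and 77%. No extra patients, visits or data are needed.

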6.3.4. Proposed Analysis

6.3.4.1 General Statistical Consideration:

The statistical software package SAS® Version 9.4 or higher (SAS Institute, Cary, NC, USA) will be used to perform all analyses and to summarize data.

The analyses described in this statistical analysis plan (SAP) are considered a priori, in that they have been defined prior to database lock. Any analyses not described herein performed subsequent to database lock will be considered post hoc and exploratory.

6.3.4.2. Handling of missing data:

For summary statistics, results will be reported based upon observed data. The study will make all possible efforts to obtain patient's follow-up data and laboratory confirmation of infection for COVID 19 disease determination. The efficacy analysis will be performed based on all observed data assuming missing as random (MAR), two selected imputation approaches are specified for the sensitivity analysis.

6.3.4.3 Primary Efficacy Analysis.

The FAS is considered. Chi-square test will be used to compare the rate of COVID-19 disease in each randomized treatment group to that of the placebo group using Dunnett's step-up method to adjust for multiple comparisons and controlling for type I error^{1,2}. Specifically, Dunnett's step-up method uses a closed gatekeeping strategy, in which the largest p value will be evaluated first at critical value of 0.05; if that fails, the second p value will be evaluated at critical value of 0.0262 (details in the sample size /power calculation section). A treatment efficacy is detected if the largest p value <0.05 or the second p value <0.0262 . The results of

efficacy analysis will be validated through two specified imputation approaches described in below

Sensitivity Analysis #1: A Tipping Point Analysis (TPA) with delta-adjusting imputation

The primary analyses for COVID 19 disease is based on the observed data and the results are valid if the missing data are missing at random (MAR), meaning that the probability of a value being missing, conditional on the observed data and factors in the statistical model, is random and not dependent on the unknown value of the missing data point.

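### SAP Table 1 prints 0.800 power at 935 per arm when both doses have a 6.8% rate; the stated design gives about 0.78, so the 80% claim holds for only one of the two tabulated scenarios

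*SAP*

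**What the plan says.** SAP section 6.4 plans for a 10% placebo rate and an average of 6.8% over the two hydroxychloroquine arms. Table 1 gives simulated power (10,000 runs) for two scenarios with that average: 7.3% and 6.3%, or 6.8% in both arms. The caption says that the sample size rests on Dunnett's "Step up method with the Haybittle-Peto boundary". That row reads 0.800 (n=900) and 0.811 (n=935) for the unequal rates, and 0.770 (n=900) and 0.800 (n=935) for the equal rates. The text after the tables concludes that "a sample size of 935 per arm will insure at least 80% power", without naming a scenario.

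A second table, introduced with "For data illustration, we have also included an" O'Brien-Fleming alternative, prints step-up power for the equal rates of 0.776 at n=935 and 0.801 at n=970.

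**The concern.** The equal-rates cell at 935 is the one that leads to 935. In the step-up row the unequal scenario already shows 0.800 at n=900, and only the equal-rates entry first shows 0.800 at n=935. (The Bonferroni row also shows 0.800 at 935, for unequal rates, but the SAP bases the sample size on the step-up row.)

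The cell is out of line with its neighbours:

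- It exceeds the O'Brien-Fleming entry for the same rates and n by 0.800 − 0.776 = 0.024. The other Haybittle-Peto and O'Brien-Fleming pairs that share rates, method and n differ by at most 0.010, and the Bonferroni pair for these rates at 935 is 0.760 against 0.761.
- Step-up exceeds Bonferroni by 0.800 − 0.760 = 0.040 here. At n=900 under the same rates and boundary the margin is 0.770 − 0.745 = 0.025.

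At stake is whether the stated 80% is met when the two doses work equally well, and so how a null result should be read.

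**Working it through.** **Inputs, all from the SAP**

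- Test: "two-sided test, chi-square test/logistic regression with odds ratio estimates", alpha 0.05 (6.4). I used the pooled chi-square without continuity correction.
- Haybittle-Peto levels: "the critical value for the interim analysis will be 0.001 and the critical value for the final analysis will be 0.05" (6.4).
- Step-up, final look: the larger p-value at 0.05; "if that fails, the second p value will be evaluated at critical value of 0.0262" (6.3.4.3). Section 6.4 rounds the second value: "if that fails, the second test will be at p value 0.026".
- Step-up, interim look: the larger p-value at 0.001; "if that fails, the second test will be at 0.0005" (6.4).
- One interim at 50%, allocation 1:1:1.
- Success: at least one dose declared effective, which is the criterion in 6.3.4.3.

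The SAP gives no second-step levels for O'Brien-Fleming. I assumed 0.00275 (interim) and 0.02576 (final).

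**Formula, final look.** With x0 placebo events and xj events on dose j, n per arm:

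z_j = [(x0 − xj)/n] / √[2·p̄(1 − p̄)/n], where p̄ = (x0 + xj)/(2n).

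Given x0, let A_j = P(p_j < 0.05) and B_j = P(p_j < 0.0262). Then

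Power = Σ over x0 of Bin(x0; n, 0.10) × [A1·A2 + B1(1 − A2) + B2(1 − A1)].

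The two-look design was simulated with 1,000,000 trials.

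**Reproducing the printed step-up cells**

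| Boundary | Rates on the doses | n | Printed | Recomputed |
|---|---|---|---|---|
| Haybittle-Peto | 7.3% / 6.3% | 900 | 0.800 | 0.799 |
| Haybittle-Peto | 7.3% / 6.3% | 935 | 0.811 | 0.815 |
| Haybittle-Peto | 6.8% / 6.8% | 900 | 0.770 | 0.764 |
| **Haybittle-Peto** | **6.8% / 6.8%** | **935** | **0.800** | **0.781** |
| O'Brien-Fleming | 6.8% / 6.8% | 900 | 0.76 | 0.765 |
| O'Brien-Fleming | 6.8% / 6.8% | 935 | 0.776 | 0.779 |
| O'Brien-Fleming | 6.8% / 6.8% | 970 | 0.801 | 0.795 |

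The Bonferroni and combined-arm cells also reproduce. Apart from the cell in bold, the largest gap in either table is under 0.008.

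**The cell in question.** The exact final-look calculation gives 0.7805, or 0.7798 with 0.026 as the second level. Adding the interim leaves it at 0.780 to 0.781.

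**Simulation error.** For 10,000 runs the standard error is √(0.7805 × 0.2195 / 10,000) = 0.0041. The gap is 0.800 − 0.7805 = 0.0195, and 0.0195 / 0.0041 is about 4.7 standard errors.

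**Other tests and definitions at 935, equal rates:** likelihood ratio 0.781, arcsine 0.782, unpooled Wald 0.781, log odds ratio 0.777, variance pooled over three arms 0.788, continuity-corrected 0.751, one-sided 0.864, no multiplicity adjustment 0.848, both doses required 0.567. None gives 0.800.

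**Sample size for 80%, equal rates:** 0.795 at 970, 0.7997 at 985, 0.8018 at 990.

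**Expected evaluable numbers.** Section 6.4 allows for 5-10% excluded from the full analysis set, so 1000 × 0.90 = 900 to 1000 × 0.95 = 950 per arm. Equal-rates power over that range is 0.763 to 0.788.

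**The case against.** The strongest reply is that the gap is small. It is 2 points of power, and at 935 per arm equal rates of 6.7% instead of 6.8% would give 0.808. The assumed 10% placebo rate is far less certain than that, the evaluable number will vary around 935 anyway, and section 6.4.1 provides for reassessing the placebo rate at the interim. All of this stands and limits the consequence. It does not make the cell right: the discrepancy is well outside simulation error, and it decides whether the 80% line is crossed.

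Three stronger readings are tempting, and the documents do not support them.

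- *The SAP contradicts itself on one design, 0.800 against 0.776.* The 0.776 belongs to the O'Brien-Fleming boundary (0.0054 and 0.0492), which the SAP includes only as an illustration. It corroborates the recomputation; it is not the same design.
- *The design misses 80% in the SAP's base case.* The SAP names an average of 6.8%, and both scenarios meet it: (7.3 + 6.3)/2 = 6.8 and (6.8 + 6.8)/2 = 6.8. Equal rates are the least favourable of the splits tried. At 935 per arm power is 0.781 for equal rates, 0.794 for 7.1%/6.5%, 0.804 for 7.2%/6.4% and 0.815 for 7.3%/6.3%.
- *The jump from 0.770 to 0.800 between n=900 and n=935, beside 0.011 in the other scenario, proves the error by itself.* The recomputed rise is about 0.016 to 0.017 in both scenarios, so the 0.011 is itself somewhat low through simulation noise. The direct recalculation is the better evidence.

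**Conclusion.** The Haybittle-Peto step-up cell for 10% against 6.8% on both doses at 935 per arm should read about 0.78, not 0.800. The unqualified 80% claim for 935 per arm holds for 7.3%/6.3% (about 0.815) but not when both doses are at 6.8%, where about 985 to 990 evaluable per arm would be needed.

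This rests on the pooled two-sided chi-square, the SAP's critical values, one look at half the information, and success defined as at least one dose declared effective. The same assumptions reproduce the rest of both tables. It is an error in a stated figure: it does not affect the type I error, the boundaries, the analysis set or the decision rule, and it does not show that the trial needs more participants.

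**What to change.** Re-run the one cell and correct it to 0.78. In the paragraph after the tables, replace the unqualified 80% statement with power by scenario, for example: at 935 per arm, the power to declare at least one dose effective is about 0.78 if both doses have a 6.8% rate and about 0.815 if the rates are 7.3% and 6.3%. Take both figures from the same re-run, so that a printed value (0.811) is not paired with a recomputed one.

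The cost is a small edit to the SAP and one stated figure that becomes slightly less favourable. Enrolment, tests and boundaries stay as they are.

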6.3 Study Aims, Hypothesis and Proposed Analysis

6.3.1 Primary Aim and Hypothesis

As noted below, the primary aim has been changed to: (based on Study Protocol dated 05/26/2020)

To determine if the use of hydroxychloroquine as preventive therapy decreases the rate of acquisition of SARS-CoV 2 infections [with clinical COVID-19 disease](#) in Study Participants [for each randomized treatment arm](#) as compared to placebo.

From: (based on original Study Protocol, dated at and after 04/06/2020)

To determine if the use of hydroxychloroquine as preventive therapy decreases the rate of acquisition of SARS-CoV 2 infections in Study Participants as compared to placebo.

Primary Hypothesis (P1): Hydroxychloroquine administered daily decreases the rate of acquisition of SARS-CoV 2 infections with clinical COVID-19 disease, compared to placebo; and hydroxychloroquine administered weekly decreases the rate of acquisition of SARS-CoV 2 infections with clinical COVID-19 disease, compared to placebo.

The **primary outcome** will be defined as clinical COVID-19 disease with laboratory confirmation of infection.

Presentation with COVID-19 symptoms during study follow-up (defined as fever $\geq 38^{\circ}$ C, or two or more non-fever symptoms that are new since the baseline) will refer participants to obtain SARS-CoV 2 testing through employee health or participants' primary care physician, with test results documented in their medical record.

Laboratory confirmation of SARS-CoV 2 infection (SARS-CoV 2 test positive) will be defined as at least one positive RT PCR, or both IgM and IgG positive serology. The lab test results can be obtained from (a) study blood samples (IgM and IgG serology), and (b) RT PCR test results ordered by a participant's primary care physician or through employee health.

All participants who test SARS-CoV 2 positive will be followed for at least 30 days after the first positive test for presentation of symptoms.

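### The stated power does not fit the per-dose wording: the protocol's 87% for each HCQ arm recomputes to about 65%, and the SAP's 80% is unlabelled power for at least one arm

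*SAP*

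**What the plan says.** SAP section 6.3.1 states the primary hypothesis for the daily dose and then for the weekly dose: "hydroxychloroquine administered weekly decreases the rate of acquisition of SARS-CoV 2 infections with clinical COVID-19 disease, compared to placebo".

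SAP section 6.4 sets out a "two-sided test, chi-square test/logistic regression with odds ratio estimates". For placebo, the calculation is "based on a 10% rate of clinical COVID-19 disease (with laboratory confirmation) in the placebo-treated group". For the active arms, the SAP assumes "an average 6.8% rate in the two randomized HCQ-treated groups". Under the Haybittle-Peto rule, "the critical value for the interim analysis will be 0.001 and the critical value for the final analysis will be 0.05". Table 1 then prints 0.800 for the step-up method at 935 per arm with 6.8% in both HCQ arms. The text after it says the method will "test each dose effect vs. placebo, and a sample size of 935 per arm will insure at least 80% power".

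SAP section 6.3.4.3 gives the step-up limits at the final look: the larger p-value at 0.05, then the smaller at 0.0262. Meeting either condition counts as detecting efficacy.

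Protocol section 8.3 uses 900 per group with O'Brien-Fleming limits of 0.0054 and 0.0492. For 10% v 6.8% it says the power "between the placebo group and each HCQ treated group would be 87" per cent. Its table adds 80% (8% v 5.4%) and 98% (15% v 10%).

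Neither document says whether power means rejecting at least one null, a given null, or both. The protocol does not state sidedness.

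**The concern.** With two active arms and a shared placebo, three different probabilities can be called power, and here they lie more than 20 points apart from highest to lowest. The protocol explicitly ties its figure to each arm. The SAP sets its figure beside a phrase about testing each dose. A reader would take both as the chance of detecting a given effective dose.

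What is at stake is the reading of a null result. On the printed figures, a dose that truly lowers disease from 10% to 6.8% would be missed about one time in five (SAP) or one in eight (protocol). If the per-arm power is about two thirds, it is missed about one time in three, and a non-significant arm is much weaker evidence that the dose fails.

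**Working it through.** **Inputs.** Rates, sample sizes and first-step limits are those quoted above. The SAP's second-step limits are 0.0005 (interim) and 0.0262 (final). Allocation is 1:1:1, so the shared placebo gives the two test statistics a correlation of about 0.5. The interim look is at half the sample.

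**Step 1: the step-up limit.** Let c1 = 1.960 (two-sided 0.05) and solve for c2 in

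2·P(|Z1|<c1, |Z2|<c2) − P(|Z1|<c1, |Z2|<c1) = 0.95, with correlation 0.5.

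This gives c2 = 2.223, a p-value of 0.0262, as the SAP has it. At 0.001 the same equation gives 0.0005, again agreeing. The protocol prints no second-step limits; the equation gives 0.00275 for 0.0054 and 0.0258 for 0.0492.

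**Step 2: reproduce the SAP's Table 1.** Trials were simulated with pooled two-sided chi-square tests, a shared placebo and both looks (Haybittle-Peto limits, several hundred thousand trials per setting).

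| n per arm; HCQ rates | Printed | At least one | Given arm | Both |
|---|---|---|---|---|
| 900; 7.3%/6.3% | 0.800 | 0.798 | – | – |
| 935; 7.3%/6.3% | 0.811 | 0.815 | 0.54 and 0.79 | 0.51 |
| 900; 6.8%/6.8% | 0.770 | 0.763 | 0.654 | 0.545 |
| 935; 6.8%/6.8% | 0.800 | 0.781 | 0.674 | 0.567 |

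For equal arms, both = 2 × given − at least one: 2 × 0.674 − 0.781 = 0.567. The printed values follow the at-least-one column. The other methods reproduce too (Bonferroni, n=900, equal rates: 0.746 v 0.745; combined arms: 0.818 v 0.819), which supports the set-up.

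**Step 3: a ceiling on per-arm power.** At the final look, step-up never rejects an arm whose p-value exceeds 0.05, and the 0.001 interim look adds very little. So a single unadjusted 0.05 test is in effect an upper limit. With n = 935 and mean rate 0.084:

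- SE under the null = √(2 × 0.084 × 0.916 / 935) = 0.01283
- SE under the alternative = √((0.10 × 0.90 + 0.068 × 0.932) / 935) = 0.01281
- Power = Φ((0.032 − 1.960 × 0.01283) / 0.01281) = Φ(0.535) = 0.704

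No per-arm reading can therefore reach 80% at 6.8%.

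**Step 4: the 0.800 cell.** The SAP used 10,000 simulations, so the standard error is √(0.8 × 0.2 / 10,000) = 0.004. The gap is 0.800 − 0.781 = 0.019, nearly five standard errors. Table 1 itself points the same way. From n=900 to n=935 this cell rises by 0.030, while the other rows that give both sizes rise by 0.011 to 0.020. The O'Brien-Fleming row prints 0.776 at 935 and needs n=970 to reach 0.801.

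**Step 5: the protocol's table.** Two-sided, n=900, limits 0.0054/0.0492 with the second-step limits from Step 1:

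| Placebo v HCQ | Printed | At least one | Each arm | Both | At least one, one-sided |
|---|---|---|---|---|---|
| 8% v 5.4% | 80% | 0.676 | 0.557 | 0.438 | 0.781 |
| 10% v 6.8% | 87% | 0.765 | 0.655 | 0.545 | 0.852 |
| 15% v 10% | 98% | 0.941 | 0.884 | 0.827 | 0.971 |

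A single unadjusted two-sided test at 0.0492 with n=900 has power 0.685, so 87% for each arm is out of reach. The SAP's O'Brien-Fleming table prints 0.76 for the same n, rates and limits, 11 points below the protocol.

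**The case against.** The best defence of the SAP is its own success rule. Section 6.3.4.3 counts either arm as success, and section 6.7 does the same at the interim. At-least-one power matches that rule and is an accepted definition in multi-arm trials. In section 6.4 the word *each* describes what is tested, and the 80% comes in a separate clause. This stands: for the SAP the defect is a missing label and one wrong cell, not a wrong choice of definition.

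Three stronger readings are tempting, and the documents do not support them.

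- *The protocol's 87% is also at-least-one power and only needs that label.* Under two-sided tests that value is about 0.76. One-sided tests at n=900 give 0.852, and the protocol does not state one-sided testing. All three rows can be matched at n=1,000, either one-sided (0.801/0.871/0.977, normal approximation) or two-sided without multiplicity adjustment (0.801/0.869/0.977). The protocol, however, states 900 and the step-up method, and does not say that either alternative was used.
- *The primary hypothesis requires both doses to work, so the trial misses its target at 57%.* The hypothesis lists two claims. Requiring both would need no multiplicity adjustment, and the plan adjusts. The both-arm figure is useful information, not a target that was set and missed.
- *The trial must be enlarged.* About 1,260 analysed per arm would give 80% for each arm, but the plan's success rule does not demand per-arm power of 80%.

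**Conclusion.** Wrong as written, in two parts.

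The protocol's 87% for each HCQ arm is overstated by about 21 points (0.655 by recomputation). It is not reproduced two-sided under any of the three definitions, and it conflicts with the SAP's own 0.76. The 8% and 15% rows are also too high: about 68% and 94% for at least one arm, and 56% and 88% for each arm.

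The SAP's 80% is unlabelled at-least-one power. Under equal rates of 6.8% and 935 per arm it is 0.78, so the claim of at least 80% fails even on that definition. It does hold for 7.3%/6.3% (0.815). A given arm has about 67%, so a truly effective dose is missed with probability 1 − 0.674 = 0.326.

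These figures assume the planned rates are true, the full 900 or 935 per arm are analysed, the interim is at exactly half, and the chi-square test is unstratified. The protocol names a stratified Mantel-Haenszel test; stratification was not modelled. The protocol's second-step limits are derived here, not printed there.

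**What to change.** No change to the sample size, tests or boundaries.

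**SAP section 6.4.** Label Table 1 *power to reject at least one null*. Correct the Haybittle-Peto 0.800 cell (n=935, equal rates) to about 0.78. Add given-arm and both-arm columns. At n=935 these are 0.67 and 0.57 for 6.8%/6.8%; for 7.3%/6.3% they are 0.54 and 0.79 for the two arms and 0.51 for both. Restate the sentence that claims at least 80% with these figures, for example: *With 935 per arm, power to reject at least one null is about 78% (6.8% in both HCQ arms) or 82% (7.3%/6.3%); under equal rates it is about 67% for a given arm and 57% for both.*

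**Protocol section 8.3.** Do not relabel the existing table. Replace 80/87/98% with two-sided values recomputed under the stated limits; the Step 5 table can serve as a check. State the sidedness and the power definition, and reconcile the 10% row with the SAP's 0.76.

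The cost is a rerun of the simulation, some wording and two extra columns. The downside is that the stated power becomes less favourable.
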